5. CONCOMITANT MEDICATIONS

5.1 Permitted concomitant Medications

Phenobarbital (as adjunctive therapy only, [see section 6.2.2.4](#))

Acetaminophen administration for analgesia or treatment of pyrexia should not exceed 48 hours, with a maximum daily permitted dose of 60 mg/kg/day.

During the weaning phase only: sedative and analgesia medications (including general and spinal anaesthesia, skeletal muscle relaxants, benzodiazepines, and short acting opioids) required prior to or during surgical, investigational and imaging procedures.

Clinical Study Code No.: CLI-06563AA1-02	Version No.: 6.0
IND No.: 131,339	Date: 18 March 2021

Any concomitant medication required for the standard care of babies will be permitted during the study.

Investigators are required to record all medications in the eCRF with the exception of the drugs listed below, unless these drugs are administered to treat an adverse event:

Multivitamins or single vitamins, iron, folic acid, calcium and phosphorus, simethicone, cream for napkin dermatitis, glycerin suppository, reflux medications, sucrose solution, dextrose gel, oral glucose gel, vaccines.

Wherever possible post-operative analgesia should avoid systemic opioids; spinal / epidural analgesia, oral / parenteral acetaminophen and NSAIDS are permissible

5.2 Non-permitted concomitant Medications

Metabolic enzyme-inducing or inhibiting drugs, or drugs known to have a well-defined potential for hepatotoxicity should not be taken.

Other drugs which may give additive CNS/respiratory depression if used in combination with opioids (benzodiazepines, skeletal muscle relaxant, anticholinergics, etc.) unless required prior to or during surgical, investigational and imaging procedures undertaken.

Other drugs or biological substances to be administered under the provisions of a protocol on the same therapeutic target. Treatments for different conditions than NOWS and NAS may be permitted following an agreement with the Sponsor. However urgent treatment should not be withheld or delayed.

6. TREATMENT(S)

The study medications will be supplied to the clinical site under the responsibility of the Sponsor, who will also provide the Pharmacist/Investigator with appropriate certificates of analytical conformity.

6.1 Appearance and Content

- **CHF6563, Chiesi liquid preparation 0.075 mg/mL for sublingual administration (Test treatment & rescue medication)**
 - Active ingredient: Buprenorphine
 - Excipients: Citric buffer pH 6, Hydroxyethylcellulose
 - Presentation: transparent solution
- **CHF6563 matched placebo, Chiesi liquid preparation, for sublingual administration**
 - Excipients: Citric buffer pH 6, Hydroxyethylcellulose
 - Presentation: transparent solution
- **Morphine sulfate injection USP 0.5 mg/mL to be used for oral administration (Reference treatment & rescue medication)**
 - Active ingredient: morphine sulfate pentahydrate

Clinical Study Code No.: CLI-06563AA1-02	Version No.: 6.0
IND No.: 131,339	Date: 18 March 2021

- Excipients: water for injection USP, sodium chloride. May contain HCl/or NaOH for pH adjustment.
- **Morphine matched placebo: Sterile water for injection to be used for oral administration**
Sterile water for injection USP is a sterile, nonpyrogenic preparation of water for injection which contains no bacteriostatic, antimicrobial agent or added buffer and is supplied only in 20 mL single-dose containers.
- **Phenobarbital oral solution USP 20 mg/5mL (adjunctive therapy)**
 - Active ingredient: phenobarbital
 - Excipients: alcohol, FD&C Red no.40, flavors, glycerin, sucrose, water
 - Presentation: red-orange clear solution

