6.2.2 Dosage

All doses of CHF6563, morphine, respective matched placebos and phenobarbital are adjusted according to the birth weight which should be rounded to the second decimal place.

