6.2.2.4 Adjunctive therapy (phenobarbital USP 20 mg/mL)

If in either group, withdrawal as assessed by the FNAST is not controlled at the maximum dose of primary therapy (CHF6563 / morphine), phenobarbital will be initiated with an oral loading dose of 20 mg/kg, followed by a daily oral dose of 5 mg/kg/day.

Birth weight will be used for the calculation of phenobarbital loading and maintenance dose.

- Treatment with adjunctive phenobarbital will continue for at least two days and stabilization should be achieved before weaning of the opioid. Weaning will commence with reduction of the primary therapy (CHF6563 / morphine) according to the same rules as indicated above in the CHF6563 and in the morphine treatment section.
- When the primary therapy (CHF6563 / morphine) has been weaned to 50% of the maximal dose and the sum of the previous three scores is <18 and no single score is ≥ 8 , the phenobarbital dose will be reduced to 2.5 mg/kg/day.
- The primary therapy (CHF6563 / morphine) dose will not be weaned on the day phenobarbital is weaned.

Clinical Study Code No.: CLI-06563AA1-02	Version No.: 6.0
IND No.: 131,339	Date: 18 March 2021

- Phenobarbital will be discontinued 72 hours after the dose reduction to 2.5 mg/kg/day, provided the sum of the previous three scores is < 18 and no single score is \geq 8, and prior to the discontinuation of the primary therapy (CHF6563 / morphine).
- The primary therapy (CHF6563 / morphine) will not be weaned on the day when phenobarbital is discontinued.

Lost doses: if a baby spits or vomits soon after administration, the administration will not be repeated in order to avoid potential over medication. A replacement dose of study medication may be considered at the discretion of the treating physician in consultation with the site Principal Investigator.

Chiesi Farmaceutici S.p.A. will supply the adjunctive therapy.

6.2.2.5 Randomized Treatment period:

- **Test treatment: CHF6563 arm**

CHF6563 0.075 mg/mL sublingual administration every 8 hours

Morphine matched placebo, oral administration every 4 hours

The maximum CHF6563 dose is 90 μ g per kilogram of (birth) body weight per day.

- **Reference treatment: morphine arm**

Morphine solution 0.5 mg/mL oral administration every 4 hours

CHF6563 matched placebo, sublingual administration every 8 hours

The maximum morphine dose is 1.25 mg per kilogram of (birth) body weight per day.

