6.3.5 Adjunctive therapy kit

A 473 mL labelled commercial bottle of phenobarbital oral solution 20 mg/mL.

Primary packaging: labelled plastic bottle of 473 mL. Instruction for use secured to the bottle with a rubber band.

Secondary packaging: not present.

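### The protocol gives two concentrations, five-fold apart, for the one phenobarbital solution that the sponsor supplies

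*Protocol*

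**What the plan says.** Three places in protocol version 6.0 give the strength of the phenobarbital solution:

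- Section 6.1, in the list of products: "Phenobarbital oral solution USP 20 mg/5mL (adjunctive therapy".
- Section 6.2.2.4, in the heading of the dosing instructions: "Adjunctive therapy (phenobarbital USP 20 mg/mL".
- Section 6.3.5, in the kit description: "A 473 mL labelled commercial bottle of phenobarbital oral solution 20 mg/mL".

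There is one kit, and section 6.2.2.4 says that the sponsor "will supply the adjunctive therapy". Neither a second strength nor a dilution step is mentioned anywhere.

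The doses are in mg per kg. Section 6.2.2.4 says that "phenobarbital will be initiated with an oral loading dose of 20 mg/kg, followed by a daily oral dose of 5 mg/kg/day", and that later in weaning "the phenobarbital dose will be reduced to 2.5 mg/kg/day". Section 6.2.2 sets the weight to use: "All doses of CHF6563, morphine, respective matched placebos and phenobarbital are adjusted according to the birth weight". The protocol outline and section 6.2.3 give the same loading and maintenance doses. No phenobarbital volume in mL is stated anywhere.

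**The concern.** A dose ordered in mg has to be drawn from an oral liquid in mL. With no volume in the protocol, concentration is the only link between the two, and the protocol gives it two values.

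Phenobarbital starts only when withdrawal is uncontrolled at the maximum opioid dose, so an overdose would fall on babies with the highest opioid exposure. Section 5.2 itself restricts other drugs that add to respiratory or central nervous depression. An underdose would leave severe withdrawal undertreated, and under section 4.4 failure of control on maximum study drug plus phenobarbital means discontinuation.

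The protocol takes care over this kind of error elsewhere. Section 1.1 raises medication errors as a problem with existing formulations, and section 6.2.1 simplifies the CHF6563 titration to avoid miscalculation. The strengths of CHF6563 (0.075 mg/mL) and morphine (0.5 mg/mL) are stated consistently. The syringe preparation and bedside volume steps in section 6.2.3 are described for those two drugs and their placebos, not for phenobarbital.

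**Working it through.** The concentrations are stated as product facts, so the plan has no calculation to reproduce. The check is a unit conversion.

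**Inputs.** Concentration A is 20 mg per 5 mL (section 6.1). Concentration B is 20 mg per mL (sections 6.2.2.4 and 6.3.5). Doses are 20 mg/kg, 5 mg/kg/day and 2.5 mg/kg/day by birth weight (section 6.2.2.4). The documents give no birth weights, so 3 kg is assumed for illustration, with a range of 2.5 to 3.5 kg.

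**Ratio.** A = 20 / 5 = 4 mg/mL and B = 20 mg/mL, so B / A = 20 / 4 = 5. Weight and dose cancel, so the ratio is 5 in every case.

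**Volumes.** Volume = dose (mg/kg) × weight (kg) / concentration (mg/mL). At 3 kg:

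| Dose | mg | mL at 4 mg/mL | mL at 20 mg/mL |
|---|---|---|---|
| Loading, 20 mg/kg | 60 | 15 | 3 |
| Maintenance, 5 mg/kg/day | 15 | 3.75 | 0.75 |
| Reduced, 2.5 mg/kg/day | 7.5 | 1.875 | 0.375 |

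The loading dose at 2.5 kg is 50 mg, or 12.5 mL against 2.5 mL. At 3.5 kg it is 70 mg, or 17.5 mL against 3.5 mL.

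**Dose delivered if the volume comes from the wrong section.** Which error is possible depends on the bottle supplied:

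- *Bottle is 20 mg/mL, volume worked out from section 6.1.* Loading: 15 mL × 20 mg/mL / 3 kg = 100 mg/kg instead of 20. Maintenance: 5 × 5 = 25 mg/kg/day instead of 5.
- *Bottle is 4 mg/mL, volume worked out from section 6.2.2.4 or 6.3.5.* Loading: 3 mL × 4 mg/mL / 3 kg = 4 mg/kg instead of 20. Maintenance: 5 / 5 = 1 mg/kg/day instead of 5.

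The delivered mg/kg figures do not depend on the assumed weight.

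**The case against.** The conflict itself is not in dispute. The strongest reply is that it is a specification slip with a conditional risk:

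- Only one direction of error can occur with the bottle actually supplied. If that bottle is 20 mg/mL, the dosing and kit sections are both right. A 100 mg/kg load would then need someone to pass over both sections and the bottle and rely on the product list. If it is 4 mg/mL, the error is an underdose, and scoring every 4 hours would show persisting signs.
- Every phenobarbital order is in mg/kg and the orders agree. The drug comes in a labelled commercial bottle, with "Instruction for use secured to the bottle with a rubber band".
- Few babies could be exposed. Phenobarbital follows four up-titrations, only 7 babies were randomized, and the trial was terminated in February 2022 (SAP 6.1 and 6.2).
- No result is affected. SAP 2.2.3 plans no inferential statistics.

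Most of this stands and limits the claim. The two mis-doses are alternatives, the label is a real safeguard, nothing in the documents shows that a mis-dose occurred, and no endpoint is said to be distorted. But none of it makes the text right. Two mentions against one do not verify the concentration, and the label protects only if it is read. The trial's end removes the future risk to its own participants, but not the need to check those already treated or to correct the protocol before any reuse.

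**Conclusion.** The protocol contradicts itself on a product figure needed for dosing. The discrepancy is exactly five-fold and rests on no assumption. The illustrative volumes rest on the assumed birth weights. The mg/kg doses are consistent and no calculation in the documents is wrong.

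The importance lies in the dosing hazard alone: a possible load of 100 mg/kg or of 4 mg/kg in place of 20 mg/kg, if a volume was worked out from the wrong section without checking the bottle. The documents do not settle which concentration is correct, and this review takes no position on it. The point must be fixed, because the ambiguity concerns a sedating drug in neonates on maximum opioid treatment and costs almost nothing to remove.

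**What to change.** 1. Read the concentration from the label of the supplied product. State that one figure in sections 6.1, 6.2.2.4 and 6.3.5, and in any dosing worksheet, before the protocol is used again.
2. Establish whether any of the 7 randomized babies received phenobarbital. SAP listings 16.2.6.3 (adjunctive therapy) and 16.2.4.12 (medications) are the place to start. If none did, the check ends there.
3. For any baby who did, compare the volume given with the dose ordered. The planned listings may not be enough. SAP 4.6.1 records actual volume for study drug, which the SAP defines as the product under test or used as reference. SAP 4.5.1 mentions only start and stop times or an ongoing flag for medications, and SAP 2.2.1 has a yes/no item for phenobarbital. Site dosing and pharmacy records may be needed.

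The cost is a text correction and a record check of at most 7 babies. No added patients or procedures are needed.

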6.2 Dosage and Administration

6.2.1 Selection of doses in the study

Based on the results of the NCT01452789 study [26], a pharmacokinetic/pharmacodynamic (PK/PD) model has been created and published [29][38][38].

The PK/PD model allowed a number of observations to be made regarding buprenorphine in NOWS:

- Efficacy of time to stabilization is driven primarily by buprenorphine exposure, implying that most of the variability in dose response has a PK basis.
- Exposure is driven primarily by changes in clearance, with no clearly identified covariates that can predict PK variability.
- There were no identifiable changes in respiratory rate associated with buprenorphine exposure.

Since in NCT01452789 there was no evidence of decline in respiratory rate in infants treated with higher doses of buprenorphine compared to lower doses, a higher initial dose may allow therapeutic buprenorphine concentrations to be reached more quickly, ultimately leading to shorter lengths of treatment and hospital stay. This hypothesis has been tested by exploring *in silico* a variety of dosing-related factors: initial buprenorphine doses (from 0.1 to 15 µg/kg), up titration rates (25%, 33% and 50%), maximum buprenorphine doses (up to 25 µg/kg) and weaning rates (10%, 15% and 25%).

Simulations results showed that the best combinations of dosing factors are the following:

- Initial dose: 8 µg/kg
- Uptitration rate: 33%
- Maximum dose: 25 µg/kg
- Weaning rate: 15%

Results of this pharmacometric approach refer to the ethanolic formulation used in NCT01452789. To account for the difference in absorption showed by CHF6563, doses derived by the PK/PD modelling were increased by a 20% factor. This CHF6563-adjusted regimen has been further adapted and simplified to avoid calculation errors, by imposing up-titration steps based on a fixed 5 µg/kg rise rather than a percentage-based rate.

Clinical Study Code No.: CLI-06563AA1-02	Version No.: 6.0
IND No.: 131,339	Date: 18 March 2021

6.2.2 Dosage

All doses of CHF6563, morphine, respective matched placebos and phenobarbital are adjusted according to the birth weight which should be rounded to the second decimal place.

6.2.2.1 Test treatment dosage

Starting dose

The starting dose for CHF6563 is 10 µg/kg (30 µg/kg/day).

Frequency of administration

CHF6563 will be administered every 8 hours (± 1 h), together with oral morphine matched placebo. Oral morphine matched placebo will be administered also every 4 hours (± 1 h), to match the morphine administration schedule.

There is a ± 1 hour interval around each nominal time point to account for sleeping and feeding schedule.

If dosing occurs at a time different from the specified nominal time (± 1 hour), the next dose will be scheduled to take place 8 hours following the actual dose administration.

Lost doses: if a baby spits or vomits soon after administration, the administration will not be repeated to avoid potential overmedication.

Dose escalation

In the up-titration phase, dose escalation will occur if the sum of 3 consecutive FNAST scores is ≥ 24 OR a single score is ≥ 12 OR a rescue dose was administered.

- No more than one dose escalation can take place each day unless a rescue dose is required.
- During the up-titration phase, doses will increase by 5 µg/kg steps, i.e. after the initial 10 µg/kg dose there can be consecutive dose increases to 15, 20, 25 and 30 µg/kg, if signs of withdrawal persist.
- The maximum dose (90 µg/kg/day) is therefore reached, if needed, after 4 up-titration steps.

Stabilization

The stabilization phase is defined as the period of treatment when no further drug treatment escalation is required. A stabilization period of 48 hours (without need for further drug treatment escalation) is required before weaning of drug treatment can begin.

Weaning

The initiation of weaning will begin after a 48 hour stabilization period, providing the sum of the previous 3 FNAST scores is < 18 and no single score is ≥ 8 .

- Doses will be decreased by 15% once per day providing the sum of the previous 3 scores is < 18 and no single score is ≥ 8 .
- If during a 24 hour period the sum of the previous 3 scores is ≥ 18 or a single score is ≥ 8 , (even if no dose escalation has been required), weaning will not take place, the current dose will continue to be administered.
- If the sum of the previous three scores is ≥ 28 and at the discretion of the treating physician, the standing dose may revert to the previous dose or dose interval at which signs were controlled.
- Once the sum of the previous 3 scores is < 18 and no single score is ≥ 8 , weaning can resume, and doses will continue to be decreased by 15% once per day.

Clinical Study Code No.: CLI-06563AA1-02	Version No.: 6.0
IND No.: 131,339	Date: 18 March 2021

- No more than one dose reduction is permitted in one calendar day.

Dose cessation

The cessation dose will be around the initial dose, (i.e. between 90-110% of the 10 ug/kg initial dose). Once this is reached, the dosing frequency is decreased from q8 to q12 hours for 24 hours, followed by a further decrease in dosing frequency from q12 to q24 hours prior to stopping.

Following cessation of dosing, babies will be observed in an inpatient setting for at least 48 hours, during which time scoring of NOWS signs will continue.

6.2.2.2 Reference treatment dosage

Starting dose

The starting dose for morphine is 0.07 mg/kg (0.42 mg/kg/day).

Frequency of administration

Morphine will be administered every 4 hours (± 1 h) together with sublingual CHF6563 matched placebo. Sublingual CHF6563 matched placebo will be administered every 8 hours (± 1 h), to match the CHF6563 administration schedule.

There is a ± 1 hour interval around each nominal time point to account for sleeping and feeding schedule. If dosing occurs at a time different from the specified nominal time (± 1 hour), the next dose will be scheduled to take place 4 hours following the actual dose administration.

Lost doses: if a baby spits or vomits soon after administration, the administration will not be repeated to avoid potential over medication.

Dose escalation

In the up-titration phase, dose escalation will occur if the sum of the 3 consecutive FNAST scores is ≥ 24 OR a single score is ≥ 12 OR a rescue dose was administered.

- No more than one dose escalation can take place each day unless a rescue dose is required.
- During the up-titration phase, after the initial 0.07 mg/kg dose there can be consecutive dose increases to 0.09, 0.12, 0.16 and 0.21 mg/kg, if signs of withdrawal persist.
- The maximum dose (1.25 mg/kg/day) is therefore reached, if needed, after 4 up-titration steps.

Stabilization

The stabilization phase is defined as the period of treatment when no further drug treatment escalation is required. A stabilization period of 48 hours (without need for further drug treatment escalation) is required before weaning of drug treatment can begin.

Weaning

The initiation of weaning will begin after a 48 hour stabilization period, providing the sum of the previous 3 scores is < 18 and no single score is ≥ 8 .

- Doses will be decreased by 15% once per day providing the sum of the previous 3 scores is < 18 and no single score is ≥ 8 .
- If during a 24 hour period, the sum of the previous 3 scores is ≥ 18 or a single score is ≥ 8 , (even if no dose escalation has been required), weaning will not take place, the current dose will continue to be administered.

Clinical Study Code No.: CLI-06563AA1-02	Version No.: 6.0
IND No.: 131,339	Date: 18 March 2021

- If the sum of the previous three scores is ≥ 28 and at the discretion of the treating physician, the standing dose may revert to the previous dose or dose interval at which signs were controlled.
- Once the sum of the previous 3 scores is < 18 and no single score is ≥ 8 , weaning can resume, and doses will continue to be decreased by 15% once per day.
- No more than one dose reduction is permitted in one calendar day.

Dose cessation

The cessation dose will be ≤ 0.025 mg/kg q4 hours.

Following cessation of dosing, babies will be observed in an inpatient setting for at least 48 hours, during which time scoring of NOWS signs will continue.

6.2.2.3 Rescue dose (CHF6563 0,075 mg/mL or morphine 0.5 mg/mL)

If, between scheduled doses, a baby has a single score ≥ 12 , a rescue dose of CHF6563 or morphine may be administered at the discretion of the treating physician.

- The rescue dose will be the same as the previous dose.
- A rescue dose must be given at least 1 hour after the previous dose and 1 hour before the next scheduled dose.
- The rescue dose must not be given once the maximum dose has been reached.
- The administration of a rescue dose in the up-titration period will trigger a dose escalation at the next schedule dose.
- The administration of a rescue dose in the weaning period will not trigger a dose escalation.
- If after cessation of therapy a rescue dose is given, the baby must be observed for 48 hours.

To maintain the blinding, both active drug as well as placebo will be administered at the same time. Chiesi Farmaceutici S.p.A. will supply the rescue medication. Rescue medication will be packed for the trial as the test treatment (CHF6563/its matched placebo) and the reference treatment (morphine/its matched placebo).

6.2.2.4 Adjunctive therapy (phenobarbital USP 20 mg/mL)

If in either group, withdrawal as assessed by the FNAST is not controlled at the maximum dose of primary therapy (CHF6563 / morphine), phenobarbital will be initiated with an oral loading dose of 20 mg/kg, followed by a daily oral dose of 5 mg/kg/day.

Birth weight will be used for the calculation of phenobarbital loading and maintenance dose.

- Treatment with adjunctive phenobarbital will continue for at least two days and stabilization should be achieved before weaning of the opioid. Weaning will commence with reduction of the primary therapy (CHF6563 / morphine) according to the same rules as indicated above in the CHF6563 and in the morphine treatment section.
- When the primary therapy (CHF6563 / morphine) has been weaned to 50% of the maximal dose and the sum of the previous three scores is <18 and no single score is ≥ 8 , the phenobarbital dose will be reduced to 2.5 mg/kg/day.
- The primary therapy (CHF6563 / morphine) dose will not be weaned on the day phenobarbital is weaned.

Clinical Study Code No.: CLI-06563AA1-02	Version No.: 6.0
IND No.: 131,339	Date: 18 March 2021

- Phenobarbital will be discontinued 72 hours after the dose reduction to 2.5 mg/kg/day, provided the sum of the previous three scores is < 18 and no single score is \geq 8, and prior to the discontinuation of the primary therapy (CHF6563 / morphine).
- The primary therapy (CHF6563 / morphine) will not be weaned on the day when phenobarbital is discontinued.

Lost doses: if a baby spits or vomits soon after administration, the administration will not be repeated in order to avoid potential over medication. A replacement dose of study medication may be considered at the discretion of the treating physician in consultation with the site Principal Investigator.

Chiesi Farmaceutici S.p.A. will supply the adjunctive therapy.

6.2.2.5 Randomized Treatment period:

- **Test treatment: CHF6563 arm**

CHF6563 0.075 mg/mL sublingual administration every 8 hours

Morphine matched placebo, oral administration every 4 hours

The maximum CHF6563 dose is 90 μ g per kilogram of (birth) body weight per day.

- **Reference treatment: morphine arm**

Morphine solution 0.5 mg/mL oral administration every 4 hours

CHF6563 matched placebo, sublingual administration every 8 hours

The maximum morphine dose is 1.25 mg per kilogram of (birth) body weight per day.

